7.2. Multicenter Studies

Not applicable.

7.3. Missing Data

Missing safety data will not be imputed.

A missing symptom score will be imputed using linear interpolation between the last available preceding value and the first following non missing value; if no following non-missing value is available, the last available value will be carried forward up to H+12. Baseline value will not be extended in case of all post baseline values are missing.

Document:	[REDACTED]	
Author:	[REDACTED]	Version Number: [REDACTED]
		Version Date: [17Feb2023]
Template No.:	[REDACTED]	Reference: [REDACTED]
Effective Date:	[REDACTED]	
[REDACTED]		

7.4. Intercurrent Events

Not applicable.

7.5. Multiple Comparisons/ Multiplicity

The following multiplicity testing procedures will be used to control the type I error:

- The secondary efficacy endpoints will be tested only if the primary endpoint is significant.
- The multiplicity of secondary efficacy endpoints will be handled using Hochberg's step-up test.
- For the other secondary efficacy endpoints and the exploratory efficacy endpoints, p-values will be provided for descriptive purpose only.
- The number of Adverse Events defined as other secondary endpoint will be analysed only with descriptive statistics (no p-value will be provided).

7.6. Active-Control Studies Intended to Show Non-inferiority or Equivalence

Not applicable.

7.7. Examination of Subgroups

No subgroup analyses will be performed for this study.

8. OUTPUT PRESENTATIONS

APPENDIX 1 shows conventions for presentation of data in outputs.

The templates provided with this SAP describe the presentations for this study and therefore the format and content of the summary tables, figures, and listings to be provided by IQVIA Biostatistics.

9. DISPOSITION AND WITHDRAWALS

All subjects who provide informed consent will be accounted for in this study.

Document:	[REDACTED]	
Author:	Version Number:	[REDACTED]
	Version Date:	[17Feb2023]
Template No.:	Reference:	[REDACTED]
Effective Date:	[REDACTED]	
[REDACTED]		

9.1. Disposition

Subject disposition and withdrawals, and reasons for exclusion from each analysis set, including inclusion and exclusion criteria will be summarized for the ENR set. The primary reason for discontinuation of study, including any of the following, will be summarized by treatment group:

- Screen Failure
- Adverse Event
- EEU challenge intolerance
- Poor Compliance to Protocol
- Study Terminated by Sponsor
- Patient Withdrew Consent
- Investigator Decision
- Death
- Other

A listing of all subjects who discontinued from the trial and their reason for discontinuation will be provided.

9.2. Protocol Deviations

Protocol deviation data will be obtained via Clinical Trial Management System Protocol Deviations (CTMS PD) log. Deviation data will be categorized as Critical, Major and Minor based on Severity. The number and percentage of subjects with any important protocol deviations will be presented for the SAF Analysis Set by treatment group.

10. DEMOGRAPHIC AND OTHER BASELINE CHARACTERISTICS

Demographic data and other baseline characteristics will be presented for the ITT and mITT.

No statistical testing will be carried out for demographic or other baseline characteristics.

The following demographic and other baseline characteristics will be reported for this study:

- Age (years)
- Sex
- Race
- Ethnicity
- Weight (kg)

Document:	[REDACTED]	
Author:	Version Number:	[REDACTED]
	Version Date:	[17Feb2023]
Template No.:	Reference:	[REDACTED]
Effective Date:	[REDACTED]	
[REDACTED]		

- Height (cm)
- BMI (kg/m²)
- Allergic symptoms scoring (TNSS-3, TOSS, TSS)
- Skin prick test (Allergen and Reaction diameter(mm))
- Patients with only ragweed positive (monosensitized) and patients with at least one allergen test positive with another allergen than ragweed (polysensitized).
- Duration of Allergic Rhinitis (years)
- Severity symptom scoring (4-7 and 8-9), which is TNSS-3 ≤7, TNSS-3 >7 at visit 2

Age, Weight, Height, BMI, Skin prick test – Reaction diameter, and Duration to Allergic Rhinitis will be summarized using descriptive statistics by treatment group. Sex, Race, Ethnicity, Allergic symptoms score, and Skin prick test – Allergen will be summarized with the number and percentages by treatment group.

10.1. Derivations

- BMI (kg/ m²) = weight (kg)/ height (m)²
- Duration of Allergic Rhinitis (years) = {(Date of Visit 1 – Start date of Allergic Rhinitis) +1}/365.25

Note: The Start date of Allergic Rhinitis will be taken from the Allergic Medical History eCRF page.

11. MEDICAL HISTORY

Medical History including Allergic Medical History information will be presented for the SAF by treatment group.

- Medical History will be coded using Medical Dictionary for Regulatory Activities (MedDRA) version 25.1
 - Medical History conditions are defined as those conditions which stop prior to or at Screening.
 - Presented by SOC and PT.

12. CONCOMITANT ILLNESSES

Not applicable.

Document:	[REDACTED]	
Author:	Version Number:	[REDACTED]
	Version Date:	[17Feb2023]
Template No.:	Reference:	[REDACTED]
Effective Date:	[REDACTED]	
[REDACTED]		

13. CONCOMITANT MEDICATIONS

Medications or vaccines will be presented for the SAF and coded using **WORLD HEALTH ORGANIZATION-DRUG DICTIONARY (WHO-DD)** version currently in effect.

See APPENDIX 2 for handling of partial dates for medications, in the case where it is not possible to define a medication as prior, concomitant, or post treatment, the medication will be classified by the worst case, i.e., concomitant.

- 'Prior' medications are medications which started and stopped prior to the first dose of study medication.
- 'Concomitant' medications are any treatments received by the subject concomitantly to the IMP or study procedure, from day 1 until day 5.

14. STUDY MEDICATION EXPOSURE

The extent of exposure will be assessed and summarized by actual treatment received within the safety population. The duration of exposure to pollen at visit 2 and visit 4 will also be presented.

14.1. Derivations

- Duration of exposure (days) = date of last study medication administration – date of first study medication administration + 1.
- Duration of exposure to Pollen (hours) = (End time of the challenge -Start time of the challenge)/60*60

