4.1.2 Visit 2 (Confirmation Ragweed Pollen Challenge)

Eligible participants will return to the EEU for a 3-hour pollen exposure. The following procedures will be performed:

- Inclusion/exclusion criteria verification
- Coronavirus disease 2019 (COVID-19) testing via a rapid antigen test for severe acute respiratory syndrome coronavirus-2 (SARS-CoV-2) infection before challenge
- Urine pregnancy testing (for WOCBP only)
- The participants will be exposed to a standard Ragweed pollen concentration of 3500 ± 500 grains/m³ for a period of 3 hours (H0 to H3).
- During pollen exposure in the EEU, participants will rate their allergic symptoms every 15 minutes, starting at zero minutes after start of challenge, until 3 hours after start of challenge. Only those participants with qualifying symptom scores (TNSS-3 ≥ 4) will be eligible to be randomized into the study. In case a TNSS-3 ≥ 4 is not achieved by H3, the participant can be challenged again if deemed appropriate by

the Investigator. If TNSS-3 ≥ 4 is still not achieved with the second session the participant is not eligible for study continuation.

- If in the judgment of the Investigator, symptoms become intolerable the participants will be removed from the EEU.
- After 3 hours of challenge: discharge from the EEU
- e-Diary completion
- Concomitant medication recording
- Participants will be questioned with regards to AEs.

Only those participants with qualifying symptom scores (TNSS-3 ≥ 4) in the last 90 minutes of the challenge will be confirmed for continuing in the study.

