4.1.3 Washout Period (≥ 15 Days)

The following information will be recorded every day preferably in the morning, via e-diary:

- Any AEs
- Concomitant medications

During the washout period of at least 15 days, any antiallergic therapy is forbidden. Please see [Section 6.8](#) for prohibited medications during the study, including the washout period.

4.1.4 Visit 3 (Randomization) Day 1

Randomization may occur within a week after completion of washout period. The following procedures will be performed on Day 1:

- Inclusion/exclusion criteria verification
- Urine pregnancy testing (for WOCBP only)
- E-diary completion
- Concomitant medication recording
- Collection of AEs
- Baseline allergic symptoms scoring
- Randomization will be performed as follows:
 - Arm A: Fexofenadine, one tablet of 180 mg in the morning for 2 days
 - Arm B: Placebo, one tablet in the morning for 2 days

4.1.5 At Home: Day 2 and Day 3 (Study Drug Intake and Diary Card Completion)

The following activities are to be completed at home in the morning on Day 2 and Day 3:

- Diary card (e-diary) completion for:
 - Allergic symptom scores, before drug intake: instantaneous assessments
 - Any AEs
 - Concomitant medications
- Study drug intake

4.1.6 Visit 4 (Test Ragweed Pollen Challenge) Day 4

The following activities are to be completed in the morning:

- Inclusion/exclusion criteria verification
- Urine pregnancy testing (for WOCBP only) before challenge
- COVID-19 testing via a rapid antigen test for SARS-CoV-2 infection before challenge
- Return study drug wallet before challenge
- Symptoms scoring before challenge
- Starting pollen challenge (hour zero [H0]): all participants will be exposed to a standard Ragweed pollen concentration of 3500 ± 500 grains/m³

If in the judgment of the Investigator, symptoms become intolerable the participants will be removed from the EEU.

- Pollen exposure will last 3 hours (H0 to H3).
 - H0 to H3: symptoms evaluation every 15 minutes
 - At H3: stop pollen exposure
 - At H3 all participants will receive one packet of fexofenadine 180 mg and will be instructed to take one tablet from the pack:
 - Arm A: single dose of fexofenadine 180 mg
 - Arm B: single dose of fexofenadine 180 mg
- H3 to H6: symptoms evaluation every 30 minutes

- At H6:
 - Physical examination
 - Vital signs
 - Nasal examination as per Investigator judgment
- Concomitant medication recording
- Participants will be questioned with regards to AEs

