6.8. Software Version

All analyses will be conducted using SAS version 9.4 or higher.

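### SAP 14.1: the formula for hours of pollen exposure converts nothing, so its result keeps the input unit under an hours label

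*SAP*

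**What the plan says.** SAP section 14.1 gives the derivation: "Duration of exposure to Pollen (hours) = (End time of the challenge -Start time of the challenge)/60*60". The divisor is not bracketed, and no unit is given for the difference between the two clock times.

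The variable feeds a planned output. SAP section 14 states: "The duration of exposure to pollen at visit 2 and visit 4 will also be presented".

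The protocol fixes the length that the formula should return. For the confirmation challenge, Protocol section 4.1.2 says: "Eligible participants will return to the EEU for a 3-hour pollen exposure". For the test challenge, Protocol section 4.1.6 says: "Pollen exposure will last 3 hours (H0 to H3".

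On software, SAP section 6.8 says: "All analyses will be conducted using SAS version 9.4 or higher". It does not say in what unit challenge times will be held. Neither document gives another formula for this duration. SAP section 3.3 puts the SAP above the protocol on statistical methods, so the line in 14.1 is the governing specification.

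**The concern.** A derivation labelled hours should return 3 for a completed challenge. Taken literally, this one returns whatever went in. The two 60s are evidently meant to be multiplied together to form a divisor, but without brackets they cancel.

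What is at stake is modest. Exposure time can vary, because the protocol (4.1.2 and 4.1.6) lets the investigator take a participant out of the exposure unit when symptoms become intolerable. The H0 to H6 window of the primary endpoint includes the three hours of exposure. A reader will therefore want to see how long participants in each arm were exposed, and this is the only planned summary visible in the documents that puts a length of time on it. A figure in the wrong unit makes that summary unreadable until someone spots the slip.

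**Working it through.** **Inputs**
- Formula: difference/60*60, labelled hours (SAP 14.1).
- Planned exposure: 3 hours at visit 2 (Protocol 4.1.2) and 3 hours at visit 4 (Protocol 4.1.6).
- Unit of the difference: not stated, so all three plausible units are tried. 3 hours = 180 minutes = 10,800 seconds.

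**Step 1: the formula as written.** From left to right, d/60*60 = (d/60) × 60 = d. The expression multiplies by 1.

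**Step 2: the planned 3-hour challenge.** The plan's own figure, 3 hours, is the target.

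| Unit of difference | Value in | As written, /60*60 | With /(60*60) | With /60 |
|---|---|---|---|---|
| Seconds | 10,800 | 10,800 | 3 | 180 |
| Minutes | 180 | 180 | 0.05 | 3 |
| Hours | 3 | 3 | 0.00083 | 0.05 |

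The formula as written reproduces 3 hours only when the difference is already in hours, and then the two 60s serve no purpose. Otherwise the labelled figure is too large by 10,800/3 = 3,600 (seconds) or 180/3 = 60 (minutes).

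**Step 3: which unit was meant.** Two factors of 60 make sense as a conversion from seconds, 10,800/(60*60) = 3. From minutes, a single 60 would do, 180/60 = 3. Seconds is therefore the unit the formula implies. This is an inference from its shape, not a statement in the SAP.

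**Step 4: could the brackets have been lost in reading the PDF?** The brackets around the time difference in the same line survived. So did those in the formulas for duration of allergic rhinitis (SAP 10.1) and tablet compliance (SAP 15.1). A lost second pair cannot be fully excluded, but nothing points to it.

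**Step 5: where the variable is used.** The primary ANCOVA (SAP 16.1.3) has treatment and the H0 TNSS-3 score at visit 4. The imputation rule (SAP 7.3) and the observed-case sensitivity analysis (SAP 16.1.5) work on symptom scores. The sample size (Protocol 9.5) rests on the AUC difference and its SD. None of these takes exposure duration as an input.

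**The case against.** The strongest reply is that this is a slip of notation. A SAP line is not program code. The hours label, the two 60s and the 3-hour challenge make the intended conversion plain, and a programmer would probably notice a 10,800-hour exposure. The factor is also constant if all times are held in one unit, so comparisons between participants and arms would keep their proportions. All of that stands, and it keeps the point small. It does not make the line correct, and two people programming from it should not have to guess the divisor.

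Three stronger readings are tempting, and the documents do not support them.

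- A reader might infer that the study will report 10,800 hours. That figure requires a difference held in seconds, which the SAP never states. Naming SAS as the software does not settle it within the documents.
- A reader might infer that this is the only output showing early departure from the exposure unit. SAP section 9.1 also lists intolerance of the challenge among the reasons for discontinuation, summarised by treatment group, with a listing of all who discontinued. That table would not give the length of exposure, and it might miss someone who left the unit early but stayed in the study. The duration summary therefore has its own value, but it is not the sole source.
- A reader might infer that the handling of missing scores or the efficacy result is affected. Neither uses this variable.

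**Conclusion.** The formula is wrong as written. It performs no conversion, whatever the unit of the input, and that conclusion rests on arithmetic alone. The size of the error depends on the unit: a factor of 3,600 if seconds, 60 if minutes, none if the difference is already in hours. Seconds is the likeliest, on the evidence of the two 60s.

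The consequence is limited to one descriptive summary at visits 2 and 4. No efficacy estimate, test, sample size or error rate changes. This is a minor correction, worth making because the output is planned and the repair is trivial.

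**What to change.** In SAP section 14.1, bracket the divisor and state the unit: duration of pollen exposure (hours) = (end time − start time of the challenge, in seconds)/(60*60). If the times will be held in minutes, the divisor is 60 alone, and the text should say so.

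The cost is one line of the SAP, with no change to design, data collection or any test. No additional table is required. SAP section 7 already provides for tables by treatment group with minimum, quartiles and median for continuous data, and these will show shortened exposure in either arm once the unit is right. A separate count of participants exposed for less than 3 hours would be a matter of preference, not part of this correction.

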15. STUDY MEDICATION COMPLIANCE

Compliance to study medication will be presented for the SAF.

A participant will be considered noncompliant if they did not take the planned doses of study drug as required by the protocol. Treatment compliance will be summarized by randomized, double-blind, placebo-control study part and by post pollen challenge, open-label study part by number and percentage of participants compliant per arm.

For Randomized, double-blind, placebo-control study part:

0% (missed both the doses), 50% (missed one dose), 100% (took both the dose), >100% (took additional dose)

For Open label study part:

0% (missed dose), 100% (took dose), >100% (took additional dose)

Document:	[REDACTED]	
Author:	Version Number:	[REDACTED]
	Version Date:	[17Feb2023]
Template No.:	Reference:	[REDACTED]
Effective Date:		[REDACTED]

The descriptive statistics of compliance percentage will be presented by treatment group.

15.1. Derivations

Randomized, double-blind, placebo-control study part:

Compliance percentage = (Number of tablets taken/2) *100

Open label study part:

Compliance percentage = (Number of tablets taken) *100

16. EFFICACY OUTCOMES

16.1. Primary Efficacy

16.1.1. Primary Efficacy Variable & Derivation

The primary efficacy endpoint is AUC (Area under the curve) of TNSS-3 from H0 to H6 at Visit 4.

The TNSS-3 is a composite score calculated as the sum of rhinorrhea, sneezing, and nasal itching scores (maximum 9). The individual scores are collected in e-diary.

The AUC will be computed using the linear trapezoidal method provided in reference section 22 (Ref 3) (22).

16.1.2. Intercurrent Event Handling and Data Imputation for Primary Efficacy Variable(s)

Not applicable.

16.1.3. Primary Analysis of Primary Efficacy Variable(s)

The primary efficacy analysis will be performed for the mITT.

The primary analysis will be the comparison of the primary efficacy endpoint (ie, AUC of the TNSS-3 from H0 to H6 at V4) between fexofenadine and placebo, using an analysis of covariance (ANCOVA) with treatment group as fixed effect and the baseline value of TNSS-3 (i.e., at H0 at V4) as covariate. The mean TNSS-3 and its 95% CI will be plotted across time from H0 to H6 at Visit 4. This plot will also include the LS mean and 95% CI of the AUC.

Document:	[REDACTED]	
Author:	Version Number:	[REDACTED]
	Version Date:	[17Feb2023]
Template No.:	Reference:	[REDACTED]
Effective Date:		[REDACTED]
[REDACTED]		

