4.0 STUDY DESIGN

4.1 Overall Design

This is a Phase IIIb, randomized, double-blind, single-center, two-arm, parallel-group, placebo-controlled, proof-of-concept study, outside of Ragweed pollen season. Two Arms are planned:

- Arm A (active 2 days): two days of pre-treatment with fexofenadine, then fexofenadine 180 mg during the test pollen challenge
- Arm B (placebo 2 days): two days of pre-treatment with placebo, then fexofenadine 180 mg during the test pollen challenge

A total of 5 visits to the study site or the EEU are planned per participant.

An adequate number of participants will be screened to achieve 96 participants randomized (86 evaluable participants). Each participant will be screened, including skin prick tests at Visit 1 (V1). Eligible participants will return to the study site for a 3-hour pollen exposure (standard Ragweed pollen concentration of 3500 ± 500 grains/m³) at V2 and discharged thereafter. Only those participants with qualifying symptom scores (Total Nasal Symptom Score of 3 symptoms [TNSS-3] ≥ 4) in the last 90 minutes of the challenge will be eligible to be randomized into the study. After a washout period of at least 15 days, randomization will occur within a week, at V3 (Day 1) in a 1:1 proportion to either Arm A (active-active) or Arm B (placebo-active) group. Randomization may occur within a week after completion of the washout period, where the participants will be instructed not to take the study drug until 2 days before their planned V4. The participants will consume study drug at home, on Day 2 and Day 3. This will be followed by a Ragweed pollen challenge lasting 3 hours (standard Ragweed pollen concentration of 3500 ± 500 grains/m³) at V4 (Day 4). During this challenge, participants in both Arms will receive a single dose of fexofenadine 180 mg after pollen exposure, at Hour 3 (H3). The participants will be discharged after the challenge at V4 (Day 4). Participants will record their symptoms using a diary card (e-diary) while in the EEU and at home thereafter. On Day 5, all participants will participate in a telephonic visit, which will be recorded as End-of-Study (EOS) Visit. For return of the e-diary, the participants will come to the study site for an in-person EOS Visit. Any emergency/pandemic concerns in the future will be minimized via use of an e-diary, which is a virtual interface, to document AEs, concomitant medications, symptoms, and the treatment satisfaction questionnaire.

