9.1 Statistical Hypotheses

In order to evaluate the additional benefit in term of efficacy of 2 days pre-treatment before the allergen exposure, the mean area under the plasma concentration-time curve (AUC) of TNSS-3 will be compared between Arm A and Arm B at V4, the following statistical null hypothesis and alternative will be tested:

- $H_0: AUC_{0-6} \text{ TNSS-3 of A} = AUC_{0-6} \text{ TNSS-3 of B}$
- $H_1: AUC_{0-6} \text{ TNSS-3 of A} \neq AUC_{0-6} \text{ TNSS-3 of B}$

The study will be positive if the null hypothesis (H_0) is rejected, and the active pre-treatment leads to lowering the symptoms compared to placebo.

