9.3.2 Primary Endpoint Analysis

All efficacy endpoints analysis will be performed on the mITT population.

The primary analysis will be the comparison of the primary efficacy endpoint (ie, AUC of the TNSS-3 from H0 to H6) between Arm A and Arm B, using an analysis of covariance (ANCOVA) with treatment group as fixed effect and the baseline value of TNSS-3 (ie, at H0 at V4) as covariate. This primary analysis will be conducted on mITT analysis population.

Table 4 Efficacy Analyses

Endpoint	Statistical Analysis Methods
Primary The AUC of the TNSS-3 from H0 to H6 at V4.	The primary analysis will be the comparison of AUC of the TNSS-3 from H0 to H6 between the Arm A and Arm B, using ANCOVA with treatment group as fixed effect and the baseline value of TNSS-3 (ie, at H0 at V4) as covariate.
Secondary 
 • AUC of TOSS from H0 to H6 at V4 • AUC of TNSS-3 from H0 to H12 at V4 • AUC of TOSS from H0 to H12 at V4 • AUC of TNSS-3 from randomization (D1) to V4 (D4) • AUC of TOSS from randomization (D1) to V4 (D4) • Safety: Frequency of AEs 	All secondary endpoints based on the AUC (ie, TSS and TOSS) will be analyzed using an ANCOVA model, with treatment group as fixed effect and the baseline values as covariate. The TNSS-3, TOSS, and TSS will be analyzed using MMRM, with treatment, time point and treatment group by time point interaction as fixed effect with their respective H0 scores as baseline covariate. The TNSS-3, TOSS, TSS, and individual symptom score by time point will be analyzed given the mean and 95% CI. Incidence of treatment-emergent adverse events will be presented in counts and percentages.
Exploratory 
 •  	The AUC (ie, TSS and TOSS) will be analyzed using ANCOVA of the exploratory endpoints, with treatment group as fixed effect and the baseline values as covariate. The analysis of exploratory endpoints will be conducted on mITT analysis population.

Abbreviations: AE = adverse event, ANCOVA = analysis of covariance, AUC = area under the plasma concentration-time curve, CI = confidence interval, D = day, H = hour, mITT = modified intent-to-treat, MMRM = Mixed Models for Repeated Measures, TNSS-3 = Total Nasal Symptoms Score of 3 symptoms, TOSS = Total Ocular Symptoms Score, TSS = Total Systems Score, V = visit.

Note: A 2-sided alpha-niveau of 5% will be applied for the primary endpoint. Additionally, a 5% significance niveau will be applied for the Hochberg approach.

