6.2. Baseline

Unless otherwise specified, baseline is defined as the last non-missing measurement taken prior to reference start date (including unscheduled assessments). Baseline of the symptoms scoring will be H0 at visit 4 value according to the analysis.

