7.1. Adjustments for Covariates and Factors to be Included in Analyses

The following covariates and factors are used in the analyses. For details of their inclusion in the models, see the specific analysis section.

- TNSS-3 at Day 1/Visit 4 H0
- (Total Ocular Symptoms Score) TOSS at Day 1/Visit 4 H0
- (Total Symptoms Score) TSS at Day 1/Visit 4 H0
- Individual symptoms score at Day 1
- Treatment group (Fexofenadine 180 mg, Placebo)
- Time point (H0 to H12)
- Treatment group by time point
- Stratification factor – Visit 2 TNSS-3 (TNSS-3 ≤7, TNSS-3 >7)

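### The primary ANCOVA adjusts for hour-zero TNSS-3 at Visit 4, which is scored after both randomised doses, so any pre-treatment effect on that score is removed from the estimate

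*SAP*

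**What the plan says.** **Comparison.** Protocol 4.1: "The participants will consume study drug at home, on Day 2 and Day 3". The Visit 4 challenge is on Day 4, and both arms take open-label fexofenadine at H3. Protocol 9.1 states the aim: "In order to evaluate the additional benefit in term of efficacy of 2 days pre-treatment before the allergen exposure".

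**Primary model.** SAP 16.1.3 specifies an ANCOVA "with treatment group as fixed effect and the baseline value of TNSS-3 (i.e., at H0 at V4) as covariate". Protocol 9.3.2 and Table 4 say the same. The general rule in SAP 6.2 is the last value before the randomisation date, but symptom scores are made an exception: "Baseline of the symptoms scoring will be H0 at visit 4 value according to the analysis".

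**Pre-dose scores.** The Day 1 procedures in Protocol 4.1.4 include "Baseline allergic symptoms scoring". SAP 7.1 lists "TNSS-3 at Day 1/Visit 4 H0" without assigning either time to a model, and also lists a Visit 2 TNSS-3 stratum (up to 7, above 7). SAP 16.1.3 settles on H0 for the primary analysis. SAP 16.2.3.1 names Day 1 as baseline only for the AUCs running from randomisation to Day 4.

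**Other analyses of the H0-H6 AUC.** No supplementary analysis is planned (SAP 16.1.4). The sensitivity analysis repeats the primary model on observed cases (16.1.5), and the exploratory stratified analysis follows the primary one (3.3). The MMRM also adjusts for H0 (16.2.3.2). Unadjusted AUCs appear only as descriptive statistics (16.2.3.2), tabulated by arm (Section 7). Both documents mark estimands as not applicable.

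**The concern.** The Day 2 and Day 3 tablets are the only planned difference between the arms. The H0 score follows both of them, so it can itself be an outcome of the randomised treatment. The AUC window starts at H0, and a lower starting score produced by pre-treatment is therefore part of the benefit being asked about. Holding H0 fixed takes that part away.

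The plan itself allows that symptoms before the challenge might respond, since it makes the AUCs from Day 1 to Day 4 secondary efficacy endpoints and adjusts them for Day 1. No passage explains why the primary model conditions on the H0 score instead. What is at stake is a real benefit that is understated or missed.

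**Working it through.** **1. The plan's own figure.** Protocol 9.5 gives SD 15, effect size 0.70 (difference 0.70 × 15 = 10.5), two-sided 5%, 90% power and 1:1 allocation.
- n per arm = 2 × (1.960 + 1.282)² / 0.70² = 42.9, so 43, or 86 in total.
- With 10% dropout, 86 / 0.90 = 95.6, so 96. Both figures reproduce.
- Exact t-test power at 43 per arm (84 df) is 89.4%.

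This is an unadjusted test of the full 10.5. The SD of 15 was taken from an H2-H12 AUC in another study.

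**2. What the planned model estimates.** Let d be the reduction in mean H0 score caused by pre-treatment, s the within-arm SD of H0, r its correlation with the AUC, and b = r × 15 / s the slope. The H0-adjusted difference is

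10.5 − b × d.

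**3. Power of the adjusted test.** Noncentral t with 83 df; residual SD 15√(1 − r²); variance factor 1 + d²/(4s²).

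**4. Illustration.** The documents give no H0 mean, SD, correlation or arm difference, so s = 1.5 and r = 0.3 are assumptions. Then b = 0.3 × 15 / 1.5 = 3 and the residual SD is 15 × √0.91 = 14.3.

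| H0 effect d (points) | Adjusted difference | Power |
|---|---|---|
| 0 | 10.5 | 92.0% |
| 0.1 | 10.2 | 90.4% |
| 0.25 | 9.75 | 87.5% |
| 0.5 (only if Arm B's mean H0 is at least 0.5) | 9.0 | 81.1% |
| No covariate, any d | 10.5 | 89.4% |

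The H0 model and the unadjusted test have equal power at d = 0.16. Over s from 1.0 to 2.0 and r from 0.2 to 0.4, this break-even runs from 0.07 to 0.28.

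**5. Upper limit.** Scores cannot fall below zero, so d cannot exceed Arm B's mean H0 score. If that mean were 0.25 (assumed), slopes of 2 to 6 would remove at most 0.25 × 2 = 0.5 to 0.25 × 6 = 1.5, which is 5% to 14% of 10.5. A slope of 6 means that a one-point H0 difference persists for all six hours.

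**6. Simulation checks.**
- With b = 4, s = 1.5 and d = 0.5 (20,000 trials), the H0-adjusted mean estimate was 8.50 with 79.5% power; the formula gives 8.5 and 79.8%. The unadjusted estimate was 10.51 with 89.7% power.
- With no effect on H0 or AUC (10,000 trials, s = 1.5, r = 0.3), the H0-adjusted model rejected in 5.4% of trials, consistent with 5%.

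**The case against.** **The H0 score may be near its floor.** It is taken at the start of exposure, out of season and after at least 15 days of washout. Significant perennial allergy that cannot be avoided is excluded at the investigator's discretion. This stands as a limit on size. On a 0-9 score with mean 0.25 the largest possible SD is √(0.25 × 8.75) = 1.48, so the rows above at SD 1.5 need a mean a little above that, and the 0.5 row needs unexposed symptoms that no passage supports. But a small SD does not make the covariate safe, because at a fixed correlation it steepens the slope. With SD 0.7, r = 0.3 and d = 0.25, b = 6.43, the adjusted difference is 8.9 and power is 80%. That slope is slightly above full carry-over, so it is a steep case.

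**The total effect can be recovered.** Descriptive AUC means and SDs by arm would let a reader compute the unadjusted difference and its t-test. True, but that is not a pre-specified test.

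**The target is a choice.** A challenge response conditional on the starting score is a defensible question. Neither document declares it as the target, however, and both the hypothesis and the sample size point to the total effect.

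**A reader might infer that no analysis anywhere tests the total effect.** The documents do not support so broad a statement, because the exploratory efficacy text is blacked out (Protocol 9.3.4 and Table 4, SAP 16.3). The statement covers the readable text only.

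**Conclusion.** The point holds. The covariate follows both randomised doses. If pre-treatment lowers H0 and H0 correlates positively with the AUC, the primary estimate falls short of the total effect by slope × H0 difference. Confidence is high for the timing and, under those two conditions, for the direction. It is not high for the size, which is unknown and may be zero; if H0 is unaffected, the covariate is harmless and adds some precision.

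Two stronger readings are tempting and are not supported. One is that a positive primary result would be suspect: the bias is usually towards no difference, and type I error is not inflated when pre-treatment has no effect. The other is that the trial is seriously underpowered: large losses need H0 effects of half a point or more, or slopes at the steep end, and the documents give no H0 data to support either.

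**What to change.** In SAP 16.1.3, replace H0 at Visit 4 with covariates measured before the first randomised dose: the Day 1 value of the score being analysed and the Visit 2 TNSS-3 stratum. Make the matching changes in SAP 6.2, 7.1, 16.2.3.1 and 16.2.3.2 for the H0-H6 and H0-H12 AUCs and the MMRM, and record the change in SAP 3.3. State which Visit 2 session defines the stratum when the challenge was repeated (Protocol 4.1.2 allows this). Keep the H0-adjusted model as a sensitivity analysis in SAP 16.1.5.

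The mITT set guarantees an H0 score but not a Day 1 score, and the interpolation rule in SAP 7.3 needs a preceding value. Add there that, for covariate use only, a missing Day 1 score is filled with the mITT mean pooled over both arms. The stratum should be available for everyone, since the ITT set requires a passed confirmation challenge.

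**Minimum acceptable change:** add a pre-dose-adjusted or unadjusted analysis of the H0-H6 AUC to SAP 16.1.5.

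**Cost.** SAP wording only, with no new data or visits. The SAP says that it supersedes the protocol's statistical methods; if Protocol 9.3.2, 9.3.3 and Table 4 are amended as well, IRB/IEC approval is needed (Protocol 10.1.1). Day 1 is also unexposed and out of season, so it may predict little. If H0 is unaffected and the pre-dose covariates predict nothing, power falls to 89.4% (82 df) from 90.6%, 92.0% or 93.8% at H0 correlations of 0.2, 0.3 or 0.4. That is a loss of 1.2, 2.6 or 4.4 points; at correlation 0.5 it is 6.5 points, from 95.9%. If the pre-dose covariates have a multiple correlation of 0.2 or 0.3 with the AUC, power is 90.6% or 92.0%.
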